RESEARCH PROTOCOL

1) Title of the Project: "In-Vivo Comparison of Different Impression Methods in Complete Edentulous Upper Jaw"

2) Importance of the Project:

Complete edentulism is a dental problem that involves the loss of all natural teeth due to iatrogenic, therapeutic or traumatic causes followed by alveolar bone resorption. The quality of life of edentulous patients is negatively affected due to functional disorders such as phonation and mastication, and their social life is negatively affected due to aesthetic deficiency (1). Today, when the socio-economic status of edentulous patients and their tolerance to treatment are evaluated, complete dentures are frequently preferred (2, 3). The large supportive tissue area in the upper jaw and the ability to provide more retention allow the problem-free use of upper complete dentures. Due to the lack of retention and mobility in lower complete dentures, patients have difficulty in using lower complete dentures, especially while eating. Recent studies have shown that mandibular two implant-supported complete dentures may be the first treatment alternative to conventional complete dentures, but implant support is generally not required for upper complete dentures (4). Complete dentures are often produced with the traditional method starting with conventional impression taking, but in recent years, digital workflow has been used following impressions taken with intraoral scanners.

The borders of the complete prosthesis and the tissues supporting the prosthesis can be recorded with different impression methods. The technique and material used during impression determines the contact of the prosthesis with the supporting tissue during rest and function, and thus the retention of the prosthesis. In dental schools, impressions of edentulous arches are usually taken using the two-stage impression method, which involves more complex clinical and laboratory steps, with the assumption of providing a better treatment (5). In this method, the initial impression is taken with metal 'stock' trays and irreversible hydrocolloid (alginate) impression material. An individual tray is produced from the plaster model obtained from the initial impression. The final impression is taken using zinc-oxide eugenol or elastomeric impression materials after border moulding with impression compound using the individual tray (6). As an alternative to the traditional two-stage impression method, a one-stage impression method with fewer clinical and laboratory steps has emerged. The one-step method uses metal-stock trays and irreversible hydrocolloid impression material. This method has been shown to produce clinically acceptable complete dentures at a lower cost (7). Among the many techniques

and materials, physicians choose the most appropriate, comfortable and cost-effective alternative for the patient's clinical situation, taking into account the case situation, impression making stages and material properties.

In a randomized controlled trial comparing single and two-stage impression methods, it was shown that patients' satisfaction with prostheses produced with the two-stage method was higher (8). In addition, when different studies comparing single and two-stage impression methods were examined in the literature, there was no conclusive evidence of the superiority of the two-stage impression method, which is accepted as the gold standard in dental textbooks (7, 9, 10).

Computer-aided design / Computer-aided manufacturing (CAD/CAM) techniques have emerged with advances in technology. With current approaches, the tissues supporting the prosthesis can be recorded with digital methods and more compatible dental prostheses can be produced with CAD/CAM techniques (11). For this purpose, the indirect digital impression method, in which the measurements taken with the conventional method or the models obtained are scanned with a laboratory scanner and digitized, is frequently used. However, the distortion that conventional impression materials undergo when they are removed from the patient's mouth and the dimensional change they undergo during the time until they are digitized can negatively affect the accuracy of the impression.(12) At the same time, inadequacies in patient comfort, the necessity of renewing the entire procedure in case of an inaccurate impression, and cost have played a role in the emergence of direct digital impressions. In the direct digital impression method, the supporting tissues are recorded simultaneously with the intraoral scanner. Initially, direct digitalization was limited to the digital impression of teeth and the production of tooth-supported prostheses. However, today, digital impressions of implants and complete edentulous arches can be taken (13, 14). However, intraoral scanners have difficulty in matching the soft tissue image in edentulous areas due to the lack of reference points and there is insufficient data in the literature regarding the success of direct digital impressions of edentulous arches.

There are few clinical studies in the literature comparing conventional and digital impression methods of edentulous arches. Lo Russo et al. compared conventional and digital impressions of edentulous jaws in a clinical study. Digital impressions were first taken from the patients with an intraoral scanner. The impression was transferred to a design program in "STL" format and a individual tray was prepared based on the model obtained from this impression. A conventional impression was taken with the individual tray and polysulfide impression material and then the impression was scanned with the same intraoral scanner. The impressions taken from the patients were compared and no

statistical difference was found. It has been shown that edentulous jaws can be recorded with direct digital impressions similar to conventional impression methods and that these impressions can be used clinically in the production of tissue-supported removable prostheses (15).

Chebib et al. compared the accuracy of different impression techniques in patients with maxillary complete edentulism in a clinical study. Twelve patients participated in the study and a total of five impressions were taken from each patient. In the ALG group, impressions were taken with a stock-tray and irreversible hydrocolloid impression material. In the ZOE group, individual tray borders were shaped with impression compound and impressions were taken with ZOE material. This group was also considered as the control group. In the PVS group, individual tray and medium-viscosity polyvinylsiloxane impression material were used. In the PVSM group, the inner surface of the impression taken in the PVS group was modified with ZOE impression material. All analog measurements were digitized with the same laboratory scanner. In the TRI group, scanning was performed with an intraoral scanner after the reference points created with composite on the maxillary soft tissue. Then, with the help of a software, the scan data were matched in a best-fit manner. As a result of the study, PVS, PVSM and TRI groups showed similar deviations and were found clinically acceptable. Irreversible hydrocolloid impression material was shown to be contraindicated for the final impression of the complete edentulous maxilla (16).

There is limited information on the comparison of the direct digitalization method used in the impression of edentulous arches with traditional impression methods and there is a need for improvement. Given this situation, the aim of this study was to expand the existing knowledge for direct digitalization in the edentulous maxilla by comparing six different edentulous arch impressions.

3) Materials and Methods:

In this study, it was planned to compare a total of six different permanent impressions obtained from patients with complete edentulous maxilla using three different conventional impression methods and three different digital impression techniques. Patient grouping was not planned in the study, and it was decided to take impressions from each patient who met the inclusion criteria under conventional and digital groups.

Physical Record (fK)=

- fK-I (ALG) (Metal stock tray and irreversible hydrocolloid impression material ("simplified tech.") (7)
- fK-II (ZOE) (Individual tray, border-moulding and zinc-oxide ojenol impression material)
- fK-III (E) (Individual tray, border-moulding and elastomeric impression material)

Direct Digitalization (dD) =

- dD-I (AI-OFF) (Direct impression with intraoral scanner and A.I off)
- dD-II (AI-ON) (Direct impression with intraoral scanner and A.I on)
- dD-III (MOD) (Intraoral scanner and scanning with OR (17) and A.I off)

All measurements will be completed in two sessions and will be performed by a single operator. The first session will last 40 minutes and the fK-I (ALG), dD-I (AI-OFF) and dD-II (AI-ON) group impressions will be completed. First, the lip and cheek will be excluded with an intraoral retractor (OptiView™ Standard Kit) and the dD-I (AI-OFF) impression will be completed by direct scanning with the intraoral scanner (TRIOS4; 3Shape A/S, Copenhagen, Denmark) with the A.I closed. Then, with the same intraoral scanner, the A.I. will be turned on and the impression will be taken again and the dD-II (AI-ON) impression will be completed. Direct scan data will be exported in "STL" format. For fK-I (ALG), the most suitable metal stock tray will be selected and irreversible impression material (TROPICALGIN; Zhermack SpA Badia Polesine (RO), Italy) will be used. Within 10 minutes of impression taking, the impression will be scanned with the same intraoral scanner. A negative of the scan data will be obtained and exported in "STL" format. The individual tray will be designed using a design program (Exocad DentalCAD 2.4 Plovdiv; Emerald Dental Works, Hamilton) and produced with a 3D printer (Photon Mono; Anycubic Tsim SHA TSUI, Kowloon)

The second session will last 60 minutes, and the fK-II (ZOE), fK-III (E) and dD-III (MOD) group impressions will be completed. For fK-II (ZOE), the individual tray will be checked in the mouth and necessary adjustments will be made. Border moulding will be done using impression compound (Kemco Tracing Sticks; Kemdent, Purton, UK) to ensure peripheral closure. The impression will be completed with zinc-oxide ojenol impression material (Impression Paste; SS White Lakewood, New Jersey). The impression will be digitized with an intraoral scanner within one hour after completion. For fK-III (E), the individual tray will be checked in the mouth and necessary adjustments will be made. Border moulding will be done with impression compound. The impression will be completed with elastomeric impression material. In the same way, it will be digitized with an intraoral scanner. dD-III (MOD), the base and wax template prepared for the patient will be arranged in accordance with the patient's occlusal vertical dimension, horizontal and vertical relationship between the jaws and aesthetic parameters. The base and wax template will be fixed in the mouth with a prosthetic adhesive. A tooth will then be selected on the upper jaw to allow for pre-scanning. The upper jaw will be scanned together with the base and wax template. The opposing jaw will then be scanned and the bite recorded. For the main scan of the upper jaw wax template from the pre-scan will be cut manually and the whole jaw scan will be completed, starting from the palate (17).

After all measurements are completed, the data obtained will be transferred to a computer software (Geomagic design X version 2016.1.0, 3D Systems Inc. Rock Hill, SC) and the comparison of different impression methods used for the edentulous upper jaw will be performed with this program. When the literature is examined, studies comparing

different impression methods taken from the upper edentulous jaw were evaluated with a similar method (15, 16).

Within the scope of this study, individuals who have completed upper jaw complete denture treatment at Hacettepe University Faculty of Dentistry, Department of Prosthodontics, have completed the controls, have been using the delivered prosthesis for 3 months and have healthy tissues supporting the prosthesis will be included in the study.

Inclusion Criteria;

- 1) Accepting voluntary participation in the study after reading the informed and voluntary consent form
- 2) Individuals with no risk factors in terms of general health status
- 3) Individuals whose complete upper jaw prosthesis has been made and delivered with known methods, whose controls have been completed, who have been using the delivered prosthesis for 3 months and whose tissues supporting the prosthesis are healthy

Exclusion Criteria;

- 1) Not accepting to participate in the study voluntarily after reading the voluntary consent form
- 2) Individuals with allergic reactions to the measurement materials planned to be used
- 3) People with systemic disorders or excessive weight loss that may occur for different reasons or dimensional changes that may occur in the tissues supporting the prosthesis due to other reasons

Sample Size and Power Analysis

PS Version 3.0 package program was used in this study. $\Delta=0.50$, $\alpha=0.05$, power of the test $1-\beta=0.80$, correlation between repetitions $\rho=0.20$ were assumed and the minimum sample size was accepted as 15. However, since working with a larger sample reduces the level of bias, it is desirable to work with as many patients as possible.

Randomization

The study was planned as a clinical study. The six different impressions planned for the edentulous upper jaw will be completed in two sessions, and the groups of impressions taken in the first and second sessions will not change. Three different groups of impressions to be taken in each session will not be subjected to randomization.

Blinding

Double blinding will be applied in the study.

1. Blinding of the evaluating researcher: The researcher will not learn which group the obtained data belongs to until the end of the evaluations.
2. Blinding of the researcher performing statistical analysis: The researcher will not learn which group the obtained data belong to until the end of the evaluations.

Data Collection (Primary Data - Secondary Data)

Primary Data:

Primary data will be collected for each case in the form of "STL" format obtained by exporting all maxillary complete edentulous jaw impressions of that case. These data will be overlaid with the help of a computer software (Geomagic design X version 2016.1.0, 3D Systems Inc. Rock Hill, SC), the fK and dD groups will be compared with each other and the differences between the groups will be recorded quantitatively.

Secondary Data:

Secondary data will be determined by an evaluation scale asked to the patient to assess patient comfort, taste, nausea, burning sensation after the completion of each measurement. By analyzing the questionnaires and evaluation scales, the opinions of the patients about different measurement methods will be compared.

Statistical Evaluation

In the study, SPSS 20 package program will be used for data analysis. In the analysis of the study, first of all, Kolmogorov Smirnov adaptation test and Shapiro-Wilk test will be used to check whether the data have normal distribution. Afterwards, parametric or non-parametric statistical methods will be used to evaluate whether there is a difference (it is foreseen that independent and dependent group tests, chi-square test, Anova test, and graphs will be given if appropriate). When evaluating the results of the tests, the significance level will be taken as $\alpha=0.05$ and the results will be interpreted according to this critical value.

“Tam Dişsiz Üst Çenede Farklı Ölçü Yöntemlerinin In-Vivo Olarak Karşılaştırılması”

-VAS SKALASI-

Aşağıdaki parametreleri alınan ölçü sırasındaki değerlendirmenize göre 1 ile 10 arasında puanlayınız.

- Ölçü sırasındaki **konfor seviyenizi** değerlendiriniz.

- Ölçü materyalinin oluşturduğu **tat hissini** değerlendiriniz.

- Ölçü materyalinin oluşturduğu **bulantı hissini** değerlendiriniz.

- Ölçü alımı sırasında ağızdaki **yanma hissini** değerlendiriniz.

- Bundan sonraki dental ölçü işlemleriniz sırasında hangi ölçü tipini tercih edersiniz?

Geleneksel ölçü yöntemi

Dijital ölçü yöntemi

REFERENCES

2. Čelebić A, Knezović-Zlatarić D, Papić M, Carek V, Baučić I, Stipetić J. Factors Related to Patient Satisfaction With Complete Denture Therapy. *The Journals of Gerontology: Series A*. 2003;58(10):M948-M53.
3. Cooper LF. The current and future treatment of edentulism. *Journal of Prosthodontics: Implant, Esthetic and Reconstructive Dentistry*. 2009;18(2):116-22.

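### In session 2, burning (and less clearly taste) left by the eugenol paste may be scored under the E and MOD impressions, and nothing planned prevents or detects it

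*Combined protocol and SAP*

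**What the plan says.** - **Session content** (3) Materials and Methods, second session): "The second session will last 60 minutes, and the fK-II (ZOE), fK-III (E) and dD-III (MOD) group impressions will be completed".
- **Order of description** (same section): ZOE comes first, "The impression will be completed with zinc-oxide ojenol impression material (Impression Paste; SS White Lakewood, New Jersey". E follows, after its own tray check and border moulding: "The impression will be completed with elastomeric impression material". MOD is third and begins with a base and wax template: "The base and wax template will be fixed in the mouth with a prosthetic adhesive".
- **Order control** (Randomization): which impressions belong to which session is fixed, since "the groups of impressions taken in the first and second sessions will not change". Within a session, "Three different groups of impressions to be taken in each session will not be subjected to randomization".
- **Ratings** (Data Collection, Secondary Data): a scale is given to the patient "to assess patient comfort, taste, nausea, burning sensation after the completion of each measurement". The plan uses the word measurement for an impression. Patients' opinions of the methods are then to be compared.
- **Form** (VAS page, in Turkish, scored 1 to 10): the burning item asks about burning "Ölçü alımı sırasında ağızdaki", that is, in the mouth during impression taking. The taste and nausea items ask about the sensation produced by the impression material.

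The documents mention no rinse, waiting time, rating before an impression or carry-over analysis.

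**The concern.** ZOE is the only one of the six methods that puts a eugenol paste on the mucosa. If it is taken first in a 60-minute visit, a patient whose mouth still burns when E or MOD is done can truthfully report burning in the mouth for those methods too. The error would run one way:

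- ZOE versus E, and ZOE versus MOD, would look smaller than they are.
- MOD would look worse than AI-OFF and AI-ON. Those scans are taken in session 1 and are never preceded by ZOE.

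A digital method could then be reported as causing a sensation that came from the paste used before it. Comparing patients' opinions of the methods is the stated purpose of the secondary data.

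**Working it through.** **The plan's own figures.** The only computed figure is the minimum sample size of 15 (Δ = 0.50, α = 0.05, power 0.80, ρ = 0.20). It names no endpoint and gives no standard deviation. A two-sided paired t-test reproduces 15 if an SD of 0.5 is assumed: SD of the difference = 0.5 × √(2 × (1 − 0.20)) = 0.632, standardised effect = 0.50 / 0.632 = 0.79, power 81.2%. None of this supplies a mean or SD for the rating scale.

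**Direction and proportion.** Let D be the true excess of ZOE over E on an item, and c the share of D still felt when E is rated.

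- Observed E = true E + cD.
- Observed ZOE − E = D − cD = (1 − c)D.
- If a share c′ is still felt at MOD, observed MOD − AI-OFF = true difference + c′D.

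The documents give no c. Over an assumed range:

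| c | ZOE − E observed | Added to E |
|---|---|---|
| 0 | 1.00 D | 0 |
| 0.10 | 0.90 D | 0.10 D |
| 0.25 | 0.75 D | 0.25 D |
| 0.50 | 0.50 D | 0.50 D |

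MOD gains the same amount only if c′ = c. It may be less, because MOD is described last.

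**Can the analysis separate it?** Take a model for session 2 with an intercept, two method contrasts, two position contrasts and one indicator for directly following ZOE: six columns.

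- All 15 patients in the order ZOE, E, MOD: only three distinct rows exist, so the rank is 3 of 6. Method, position and carry-over are inseparable.
- Three rotated orders, 5 patients each: rank 6 of 6.
- All six orders, 18 patients: rank 6 of 6.

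With the order fixed as described, no choice of test recovers the method effect. Nor do more patients: the terms cD and c′D do not depend on the number enrolled, so the Sample Size section's remark that a larger sample reduces bias does not apply here.

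**Which items are exposed?** The burning item asks about the mouth and names no material, so residual burning fits it. The taste item asks what the impression material produced, which partly protects it. The MOD adhesive may also have a taste of its own, so a taste difference between MOD and the session-1 scans need not come from ZOE.

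**The case against.** **The sequence is not stated.** A reader might infer that ZOE is laid down as first in every patient. The text does not go that far. Session 1 uses explicit ordering words for its scans and session 2 uses none between methods. In session 1 the opening list names ALG first although the AI-OFF scan is done first, so such a list does not prove sequence. This stands. What remains is that the detailed session-2 account runs ZOE, E, MOD, and that if this is not the order, the plan gives none.

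**Carry-over is not shown.** A reader might also take it as certain. The documents do not say how long eugenol burning or taste lasts, and they put work between ratings: a tray check and border moulding before E, and template adjustment, adhesive, a pre-scan, an opposing-jaw scan and a bite record before the MOD main scan. The form's general instruction also ties every item to the impression being taken. This stands too: it is a risk, not a demonstrated bias.

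**No false-positive rate can be attached.** It is tempting to assume, say, a true burning mean of 1 with SD 2 for E and the scans. On a 1-to-10 scale the largest possible SD at mean m is √((m − 1)(10 − m)), which is 0 at m = 1. An SD of 2 needs a mean of at least about 1.47, even with every score at 1 or 10. Rates built on such inputs describe data that cannot occur.

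**Reach.** This point does not extend to the STL comparison, which is the primary data.

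**Conclusion.** The point holds as a risk to the secondary ratings. If session 2 follows the order in which it is described, residual burning from the paste, and less clearly residual taste, may be counted against E and MOD, and the design could neither show nor remove it. The direction is clear: ZOE versus E shrinks, and MOD rises relative to AI-OFF and AI-ON. The size cannot be derived from the documents. The conclusion assumes that the described order is the actual one and that some sensation outlasts the interval between impressions. It warrants a small change because prevention is cheap and later correction is not possible.

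**What to change.** In the second-session text of Materials and Methods:

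1. State the sequence, with ZOE last. The text describes no step of E or MOD that needs the ZOE impression.
2. Have the patient rinse and complete the form for one method before the next begins.
3. Add a burning score and a taste score immediately before each session-2 impression, and say in Statistical Evaluation that these will be reported by method and used to adjust the ratings.

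Placing ZOE last removes its path into E and MOD. It does not make method and position separable, because the order is still fixed; the scores before each impression are there to show whatever residue remains.

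**Cost.** A few sentences and two short items on the form, with no added visit, impression, staff or patient. There are two downsides. ZOE then carries any end-of-session fatigue. Any method taken after MOD also needs the adhesive residue removed first, so that neither the impression nor its ratings are affected; the plan describes no such removal, so it must be written in.

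### AI-OFF is always scanned before AI-ON, so the effect of the AI setting cannot be separated from scan order

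*Combined protocol and SAP*

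**What the plan says.** Section 3 (Materials and Methods) puts every patient through all six impressions, without patient groups. A single operator takes them in two sessions. Session 1 holds ALG, AI-OFF and AI-ON, and the sequence of its two scans is explicit: "First, the lip and cheek will be excluded with an intraoral retractor (OptiView™ Standard Kit) and the dD-I (AI-OFF) impression will be completed", followed by "Then, with the same intraoral scanner, the A.I. will be turned on and the impression will be taken again".

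The Randomization subsection fixes the content of the sessions ("the groups of impressions taken in the first and second sessions will not change") and adds: "Three different groups of impressions to be taken in each session will not be subjected to randomization". For session 2 the text says that "the fK-II (ZOE), fK-III (E) and dD-III (MOD) group impressions will be completed" and describes them in that order. It does not say whether this is the sequence, or whether it is the same for every patient.

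Under Data Collection, the patient completes a scale "to assess patient comfort, taste, nausea, burning sensation after the completion of each measurement", so the ratings follow the order of the impressions. Under Statistical Evaluation, "parametric or non-parametric statistical methods will be used to evaluate whether there is a difference"; families of tests are listed, but no order or period term. No repeat scan or reversed-order subset is planned. Blinding covers the evaluating researcher and the analyst.

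**The concern.** The stated aim is to compare six impressions, which gives 6 × 5 / 2 = 15 pairs. AI-OFF versus AI-ON is one of them, and it is the pair whose members are described as differing only in a scanner setting. Because the order never varies, anything that changes between a first and a second scan of the same arch (operator or patient familiarisation, fatigue) enters this comparison in full. A difference in deviation or in comfort could come from the AI setting, from the order, or from both. An order effect of opposite sign could cancel a real difference.

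Blinding does not help, because order acts on the operator and the patient while the scan is made. The third digital method (MOD) also has the AI function off, but it does not break the link, since it uses a different technique in a different session.

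**Working it through.** **1. The plan's own figure.** Sample Size and Power Analysis gives Δ = 0.50, α = 0.05, power 0.80, ρ = 0.20 and a minimum of 15 patients, with no SD. So 15 cannot be confirmed from these inputs alone. For a two-sided paired t-test, SD_diff = SD × √(2(1 − ρ)) = SD × √1.6.
- If SD = 1 (assumed), SD_diff = 1.265, power at n = 15 is 29.7%, and 53 patients are needed.
- If SD = 0.508 (assumed), SD_diff = 0.643, Δ / SD_diff = 0.50 / 0.643 = 0.78, and n = 15 gives 80% power.

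The value 0.78 used below is therefore the standardised difference detectable with 15 patients. It is not the plan's Δ. The aliasing in step 2 does not depend on it.

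**2. Can the two effects be separated?** Take the two scans in 15 patients, with 15 patient columns, one AI column and one scan-position column (17 in all).
- Order as planned: the AI and position columns are identical and the rank is 16. Only the sum of the two effects can be estimated, at any n.
- Order split 8:7: the rank is 17, and both effects can be estimated.

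For all six methods, use patient, method and position effects, with ALG assumed third in session 1 and session 2 assumed to run ZOE, E, MOD.

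| Order | Rank | Pairwise contrasts estimable (of 15) |
|---|---|---|
| As planned | 20 | 0 |
| The two scans vary | 21 | 1 (AI-OFF vs AI-ON) |
| ZOE and E vary as well | 22 | 2 (plus ZOE vs E) |

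**3. False positives from order alone.** No AI effect; order shift g in units of SD_diff; two-sided paired t-test at 0.05; noncentrality g√n. The documents give no value for g, and n = 30 is also an assumption, included because the plan wishes to recruit as many patients as possible.

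| g | n = 15 | n = 30 |
|---|---|---|
| 0 | 5% | 5% |
| 0.1 | 6.5% | 8.3% |
| 0.25 | 14.7% | 26.3% |
| 0.5 | 43.8% | 75.4% |

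A larger sample makes the problem worse.

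**4. Masking at n = 15.** True difference 0.78 SD_diff, order shift of opposite sign, noncentrality (0.78 − g)√15.

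| g | Noncentrality | Power |
|---|---|---|
| 0 | 3.02 | 80.2% |
| 0.1 | 2.63 | 68.8% |
| 0.25 | 2.05 | 48.1% |
| 0.5 | 1.08 | 17.3% |

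**5. Cost of varying the order.** With an 8:7 split, the AI effect is half the difference between the two order groups in mean second-minus-first difference. Its SE is (SD_diff / 2) × √(1/8 + 1/7) = 0.2588 SD_diff, against SD_diff / √15 = 0.2582 SD_diff for the simple paired test. Degrees of freedom fall from 14 to 13. Power at 0.78 SD_diff is 79.6% instead of 80.2%.

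**The case against.** The strongest reply is that no harm is shown. The documents give no order effect, no direction and no mechanism. Learning by the single operator from one patient to the next would not be aliased with the AI setting; only a shift from first to second scan within a patient would be. The error rates above rest on assumed shifts, and 0.78 SD is derived from n = 15 and is not stated in the plan. If each SD were 1, power would be about 30% before any order effect arose. All of this is right, and the figures should be read as illustration. It does not touch the aliasing, which holds whatever the size of the order effect.

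Second, this pair is not named as primary. The primary-data text can be read as conventional against digital, and the preference item offers only those two options. However, the aim covers six impressions, and AI-OFF and AI-ON are defined as separate groups, so the pair is in scope.

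Third, the remedy frees only 1 of 15 contrasts. That is true, but it is the contrast for which nothing in the text requires a fixed order. Neither scan needs a tray or an impression material, and both use the same scanner in the same session.

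Last, the absence of randomisation is openly stated. Stating it does not make the comparison interpretable.

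**Conclusion.** The concern holds. As planned, AI-OFF versus AI-ON is completely confounded with first versus second scan, for the scan data and for the comfort rating. This follows from the stated sequence and needs no numerical assumption. Once the data are collected in this order, the AI effect can be recovered only by assuming that there is no order effect.

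The practical size is unknown. For assumed shifts of 0.1 to 0.5 SD of the paired difference, the false-positive rate at n = 15 would be 6.5% to 44%, and power of 80% could fall to between 69% and 17%. The defect affects one stated comparison and not the whole study, and it can be avoided at almost no cost. The change should be made before recruitment starts.

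**What to change.** Replace the sentence that excludes randomisation within sessions with text such as:

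> Session membership is fixed. In session 1 the order of dD-I and dD-II is allocated 1:1 from a prepared list, both before ALG. The order is recorded, and scan order is included as a term in the AI-OFF versus AI-ON comparison.

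State how the list is made. A random balanced list is preferable, although strict alternation would also separate the two effects. If the non-parametric route is taken, compare the second-minus-first differences between the two order groups with a rank-sum test. Either analysis removes an additive order effect; neither removes unequal carry-over.

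State the session 2 sequence as well and, where the tray workflow allows, vary ZOE and E in the same way. Add as a limitation that all other contrasts stay confounded with position or session: every cross-session contrast, ALG versus either scan, and MOD versus ZOE or E.

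The cost is a one-page list, one recorded variable, one model term and one degree of freedom (14 to 13 at n = 15). The operator has to follow the list. No extra impressions, visits or staff are needed.
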